## 11. RECRUITMENT

Recruitment for Phase I and II will be done via follow-up phone calls conducted by the parent study (the parent grant staff call women to schedule follow-up visits as well as to maintain their current contact information, given that the parent study is a longitudinal study, collecting data at 6, 12, and 18 months follow-up after baseline). When called, if participants indicated interest in being told about future studies in which they may be eligible in their consent form, participants will be told about this interview study, and those indicating willingness to be considered for participation. *The parent study has incorporated this recruitment procedure into their protocol. Parent study participants will complete an addendum to their consent form at 6 months follow up which describes this study, asks about their interest in being contacted about this study, and if they agree to having their data shared with this study. Only those indicating agreement with these aspects will be contacted to ascertain interest in participation.*

### Phase I (Aim 1)

Women (n=30) from the parent study indicating willingness to be considered for participation in a sub-study during regular follow-up phone calls, and who report interest in becoming participants in the ESTIMA intervention (Phase II) will be contacted to participate in qualitative interviews.

### Phase II (Aims 2-3)

From the parent study, we will recruit a total of 120 participants in expectation to afford a final sample size of at least 48 in each group (using a conservative estimate of 80% retention). The microfinance groups of women (approximately 10 per group) will be formed and randomized to intervention or wait-list control condition using a randomizer software package, after baseline data collection for ESTIMA. The wait-list control group will be provided with referrals to local FSW support organizations, as the standard of care, and will receive ESTIMA subsequent to the 12 month follow-up data collection. ESTIMA will involve groups of approximately 10 women each; groups will initiate once sufficient numbers are enrolled (i.e. groups will be staggered in terms in initiation).

Additional recruitment, using the same venue-based sampling protocol as the parent study, will be conducted as needed in order to meet final sample size expectations. Briefly, participants will be recruited from areas in which sex work occurs

in Tijuana. They will be recruited based on information gained through informal conversations with participants on where to recruit other female sex workers (FSWs) and the knowledge of our study staff, who are familiar with the FSW population. We will recruit female sex workers aged 18 years old or older in Tijuana. Recruitment will be conducted by trained study staff who have worked previously for the parent study and who have experience working in these contexts with this population for a number of years. Furthermore, a minimum of two staff members will go together for recruitment at any time in order to ensure safety. Recruitment staff will also carry identification badges and use identifying shirts to decrease risks, which has shown to be helpful in recruitment for the parent study as well. We will follow time-location sampling to ensure a diverse sample – with recruitment venues and the times at which these sites are frequented changing as the study proceeds. With the help of trained study staff, we will update our existing maps of bars, brothels, hotels, alleys and street corners with sex work activity. We may also choose to allow participants of the study to help identify new sites for recruitment as well as to refer potentially eligible FSW who are interested in the study by providing the study phone number. (Some participants have asked if they can tell their friends about the ESTIMA program and study as well.) In addition, we may provide some incentives (up to an equivalent of \$5 per person recruited) for ESTIMA participants to tell other FSW about the study as a means to recruit additional women. All participants will go through the same screening procedures, informed consent and randomization. Participants will not know the details about the eligibility criteria. We will remind participants to not share details about their participation in ESTIMA or anyone else's participation in ESTIMA with friends or anyone else in a way that would compromise the identity of any participant.

In addition to the baseline assessment (which involves a separate survey at baseline for those recruited outside of the parent study and the extraction of data from the parent study 18 month follow-up from those recruited from the parent study), we will ask participants to fill out a supplemental survey (to collect greater detail on alcohol use frequency and experiences of discrimination that is not collected in the parent study survey, but important to measure in terms of the impact of ESTIMA) which will take an additional 5-10-minutes and will be implemented at the time of informed consent or at another time as preferred by the participants. We will collect these additional assessments using the same survey (including these additional measures) at 6 and 12 months follow-up independent of the parent grant. We will also collect these same assessments for those participants recruited outside of the parent study. The assessments will be incorporated into the larger survey for their baseline assessment.

**Participant Follow-up and Tracking:** Similar to the parent study, this last follow-up assessment will also be conducted at the study site. We expect that since we recruited participants at the 18 month follow-up from the parent grant that they may be among those who were most available for follow-up (since they were not lost to follow-up in the parent grant by 18 months). Other important suggestions from the parent grant for ensuring good follow-up include participant reimbursement for participation, a non-coercive approach, and easy access to the clinic for FSWs from their place of work/residence.

1. The participant recruited during baseline will be advised in her first contact that she will be followed for 2 additional follow-up surveys and STI/HIV testing. She will be told that she is expected to undergo an interview and a free gynecological exam and blood test at this visit, similar to how she has participated in the parent study.
2. The participant will also be asked at her first visit to provide us with the name and telephone number of a contact (girlfriend, fellow worker, bar manager) whom we may contact if we have difficulty locating her for this additional survey and STI/HIV testing. We will provide a small reimbursement (in-kind goods valued at \$5) for her to return in between study visits to update or confirm this information.
3. It is critical when working with this population to develop strong bonds of trust and confidence. To this end, project staff in each research site have been carefully chosen for their sensitivity, discretion, and understanding of the needs of the target population. As possible, we will hire the same staff from MAPA de Salud to conduct the final survey and STI/HIV testing protocol.

FSWs will be advised at their first visit that if they move away, they will be provided with a bus ticket or voucher to get them back to the US-Mexican Border Health Commission for their follow-up visit (if they have moved 100 miles or less from the agency's site).

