**In Tijuana and across Mexico, poor economic conditions contribute to women's involvement in sex trade, and also heighten sexual and drug related HIV risks among FSW.** Among FSW, economic urgency (e.g. debt, inability to provide for the needs of children or other family) has been identified as a primary factor for HIV risk, and linked to (1) increased unprotected sex (e.g. agreeing to unprotected sex trades in exchange for more money) and (2) increased experiences of gender-based violence (GBV). Forms of GBV experienced by FSW include physical and sexual violence from managers, clients and police, as well as from male partners. All of these forms of GBV reduce women's negotiating power to avoid dangerous clients/situations and unprotected sex. Economic urgency also increases women's drug-related HIV risks (e.g. reducing negotiating power when buying drugs and resulting in being "second on the needle," sex trade for drugs which also reduces condom negotiating power).

Across the global south, only one tested intervention (***Intervention with Microfinance for AIDS and Gender Equity, IMAGE***), which included incorporating gender equity mobilization (community mobilization to alleviate gender inequity) into an existing microfinance program, has documented improvements in both GBV and reduced HIV risk behaviors among women; The IMAGE program in South Africa demonstrated significant improvements in economic indicators, reduction in reports of GBV by more than half, and a reduction in HIV risk behavior as well (e.g. decreased unprotected sex with non-spousal partners).

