### **14. POTENTIAL RISKS**

Overall, The potential risks to study participants are: 1) disclosing personal information to members of the research team, or 2) the inadvertent disclosure of sensitive information about subjects (e.g. sexual risk information, history of STI, gender-based violence, GBV). During Phase II, HIV/STI testing may pose some risk to participants as well. However, we have taken needed steps to reduce these risks.

Interviews and quantitative surveys may contain topics that are embarrassing or emotionally upsetting to participants as they cover a number of sensitive subjects, including sexual risk topics, STI history, and exposure to violence. It is possible that some participants may become anxious, depressed, or angry due to this content. Survey interview participants are at the greatest risk for becoming emotionally distressed as they are being asked to disclose information about their personal life to another person. There is also a small risk that participants may become upset or angry by the content of research questions that they may become at risk of harming themselves or others.

As a result of participating in this study, it is possible that women may be identified by others as a FSW. (Also, see section on confidentiality below for a detailed description of risks related to a loss of confidentiality). There is a small risk of violence or harassment related to the conduct of the protocol, for example, if the participants' status as a sex worker becomes known. Violence unrelated to the protocol that is incidentally communicated during the information gathering associated with the protocol may be reportable to civil authorities under applicable Mexican local law if the woman so chooses, but would not be reportable as a research-related adverse event. There is some risk that interviewers or counselors will receive reports of physical abuse and violence perpetrated against FSW by clients or other sex partners.

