Additionally, learning of a positive HIV/STI test result would also likely be emotionally upsetting to a participant. It is possible that some participants may become anxious, depressed, or angry due to these experiences, and there is a very small possibility this may result in their becoming a risk to themselves or someone else. Our experience from our previous work, which used similar survey items and approach, elicited no such responses. However, to ensure the safety of our participants and staff, precautions will be taken to minimize participants' risk of emotional distress.

Finally, because study participation involves being part of a microfinance program, women will take on risks associated with being part of this program, namely, those associated with taking out a loan. The Via Microfinance program will support women as much as possible so that they are successful. However, women are responsible for repaying the loan and some participants may face challenges repaying their loan due to personal circumstances. It could be that some participants will use their work in sex trade to repay the loan. This could heighten the urgency of women's work in sex trade and reduce negotiating power with clients (e.g. in terms of condom use). It could also increase the frequency of women's work in sex trade, e.g. by taking more clients in order to repay this small loan. Taking on more clients could introduce risks related to new clients (such as risks related to violence or exposure to HIV or other STIs). Furthermore, taking out a loan may be risky if women have pimps, money lenders, male partners or others who control their work and find out that women are participating in this program. This could result in women's loss of the loan money (e.g. if these people retrieve the loan money from the women).

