*Risks associated with taking out a microfinance loan:* Our microfinance partner, Via Microfinance, provides over 300 loans a year to poor women in Tijuana to support them to start a business. The repayment rates are 90% or greater. If women need more time to pay loans back, they will be able to work with the lender to develop a schedule for paying the loans back. Loans that are not paid in full, even in cases when more time is provided for pay-back, will result in higher interest charges on subsequent loans to the group or denial of requests for subsequent loans. If a participant defaults on repayment, they will face high interest rates if they proceed to take out more loans. We do not expect that the initial \$2,500 pesos will be difficult for women to repay. Women may also use sex work to supplement their income if they are having trouble paying these loans back as well, which could increase the frequency of their sex trades. To address these issues, Via microfinance will support women on all aspects. Via has a strong record for supporting women in their microfinance groups and they have extremely high rates of repayment. Via has the capacity to work with women to manage their repayment schedules as well. Finally, women can choose to take out less than the \$2,500 pesos amount if they feel concerned and they can take out more as they see fit (after they pay back the initial loan). Women may also fear that pimps, male partners, or others may learn of their involvement in this program and try to take the loan money away from them or require that they use the money for some other purpose. To further address these risks, we will include these issues in our formative work in Aim 1, Phase I interviews and we will also consult our community advisory board as we prepare to initiate the ESTIMA program. We will be able to recruit women who do not report pimps and who report having control over their money earned (e.g. women who do not report having to give some portion of their salary to brokers or pimps), based on responses to items in the quantitative survey (from the MAPA de Salud study). Finally, we will address this issue during study initiation, trainings, and upon provision of the loan money to women. We will encourage women not to discuss their study involvement and access to this loan money with others, especially with pimps, brokers, or others who may try to take control over the money and/or women's business initiation. Notably, only 4% of women from the study sample reported having pimps or managers who make money from their earnings. We will also monitor the repayment on these loans closely. By staggering these groups over time, we will also be able to alter the program in ways to best address this issue over time (i.e. if this is an issue at all for the first group of 6, we will implement changes to address this prior to initiating the next group of 6). Given that *Via* has had over a decade of experience working with poor women in Tijuana and providing loans, they have experience in helping women develop schedules for paying these loans back.

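### The tracing procedure suggests a bar manager as a locator contact, which conflicts with the protocol's own warnings about people who control a woman's work learning that she takes part

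*Combined protocol and SAP*

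**What the plan says.** Section 11 (Participant Follow-up and Tracking) has each participant, on first attending, "provide us with the name and telephone number of a contact (girlfriend, fellow worker, bar manager) whom we may contact". The contact is for use when she proves hard to locate for a later survey and STI/HIV test.

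Other sections describe the danger of disclosure:

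- Section 7 says that violence against these women includes "physical and sexual violence from managers, clients and police".
- Section 14 says that "taking out a loan may be risky if women have pimps, money lenders, male partners or others who control their work". The trigger is that these people discover that she takes part, and the consequence it names is loss of the loan money. It also states: "There is a small risk of violence or harassment related to the conduct of the protocol".
- Section 15, on the risks of the microfinance loan, states: "We will encourage women not to discuss their study involvement and access to this loan money with others, especially with pimps, brokers, or others". The people meant are those likely to seize the money or the business.
- Section 16, on confidentiality within the group setting, commits to every effort to keep confidential both sex-work status and participation in the study.

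**The concern.** The protocol encourages women to keep their participation from people with power over their work or money. Its locator request, meanwhile, suggests as a contact someone who may hold exactly that position. A call from study staff to such a person, however discreet, could show that the woman is in a study. A step meant to protect retention could then contribute to the harm that Section 14 foresees, at worst loss of the loan money or harassment. What is at stake is participant safety and consistency within the protocol. No estimate, sample size or analysis depends on it.

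**Working it through.** This is mainly a comparison of texts. The plan gives no figure for tracing calls or for harm from them, so there is none to reproduce.

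**1. Could a bar manager be one of the people warned about?** Sections 14 and 15 do not name bar managers in their warnings. Section 14 does include a general class, others who control the women's work. Section 7 lists managers as perpetrators of violence. The survey described in Section 9 asks about the relationship with a pimp or manager, including financial independence and control over client selection. So the protocol itself treats a manager as someone who may control the work. Some bar managers will fit that description and others will not.

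**2. Do the stated safeguards close the gap?**

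| Safeguard | Where | What it leaves open |
|---|---|---|
| The woman names the contact | Section 11 | The prompt itself suggests a bar manager |
| Permission for tracking methods, obtained at enrolment and kept current | Section 9, Survey/Specimen Data Collection | The example given is friends; no check that the named person is safe to call |
| Staff trained to be discreet with people on locator forms and not to mention results or eligibility criteria | Section 9, counselling and referrals | Written for the return of test results; does not expressly cover the fact of participation |
| Women must have agency over their earnings | Section 10 | Screens control of earnings, not control of the workplace |
| Every effort to keep participation confidential | Section 16 | A general commitment with no rule for calls to contacts |

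Each safeguard narrows the gap. None excludes a workplace controller as a contact, and none expressly tells staff not to reveal participation to one.

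**3. How many women?** Inputs: 120 enrolled, 60 per arm, 80% retention (Sections 9 and 11), and 4% of the parent-study sample with pimps or managers who take earnings (Section 15).

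- Planned loss: 120 × (1 − 0.80) = 24 across both arms, or 12 per arm. This matches the planned 60 − 12 = 48 per arm at the end.
- 4% of the 60 women in the loan arm: 60 × 0.04 = 2.4.
- 4% of the 12 planned losses in that arm: 12 × 0.04 = 0.48.

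The last two lines only illustrate scale. The 4% precedes the Section 10 exclusion, so fewer such women should enter the trial. It also counts people who take earnings, not everyone who controls a workplace, so it is not an upper limit. The 24 is a planned loss and does not count tracing calls, still less calls to managers.

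**4. Does the timing overlap with the loan?** The first loan is due within 4 months (Section 9), and the follow-up surveys come at 6 and 12 months. The overlap with the first loan is therefore limited, but it exists: locator forms are also used to find women who do not return within a month for test results, and Section 15 allows longer repayment schedules and further loans.

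**The case against.** The case against is substantial. A bar manager is one of three bracketed examples, the woman makes the choice, and she can update it between visits. Eligibility excludes women whose earnings are controlled by others, and the 4% figure suggests that few had such a person to begin with. The loss described in Section 14 depends on the controller learning of the loan programme, and a discreet call about a health study need not reveal a loan. Sections 12 and 16 report no breach of confidentiality in the parent study. Section 16 also foresees a policies and procedures manual. Neither that manual nor the locator form is available here, and either might already contain a script.

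Most of this stands, and it limits the size of the problem. It does not remove the inconsistency. The prompt influences whom women name, and the eligibility rule does not cover control of the workplace. The parent study's record carries over only in part: the documents describe that study as survey and testing research. They mention no loans in it, although they do not say outright that there were none.

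A reader might infer that about 24 women would have a manager called, or that all 120 are at risk. The documents support neither. The first is planned loss in both arms; the second is simply the number of women asked for a contact.

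**Conclusion.** The point holds as an inconsistency in participant protection that should be corrected. The locator request in Section 11 suggests a type of contact that conflicts with Sections 7, 14, 15 and 16, and the safeguards are partial. The number of women exposed is probably small and cannot be fixed from the documents. This rests on two assumptions: that some bar managers control the work of women who keep their own earnings, and that the unseen manual and locator form add no rule on safe contacts.

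A stronger reading, that the protocol directs staff to disclose participation to managers or leaves women unprotected, is not supported. The contact is the woman's choice, permission is obtained, and staff are trained in discretion.

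**What to change.** Four small changes:

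1. In Section 11, delete bar manager from the examples.
2. State there that the contact must not be someone who controls the woman's work or who takes or controls her earnings. Friends and fellow workers remain allowed. The wording should not bar everyone who shares in her work, since that would exclude fellow workers.
3. Add a line to the locator form on which she confirms that this person may safely be called, and recheck it whenever the contact is updated.
4. Extend the discretion rule in Section 9 to every call to a contact, so that staff mention neither ESTIMA, the loan nor sex work, in addition to results and eligibility criteria.

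The cost is a few sentences, a locator-form edit and a short addition to staff training. Sample size, endpoints and analysis do not change. A few women may lose one tracing route; other contacts, the paid locator updates and the outreach workers remain.
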